8.4.6 End of Study (Visit 6, Month 12)

Treating physicians will perform and record details of the last visit as described in Section [8.4.5](#). Patients will continue to be treated as directed by their physician. Patients will be asked to return any diaries; after this visit no further data will be collected. Patients will be asked at the end of study visit which they found easier to use a) the FlexTouch[®] pen or b) previous injection method.

End of the study will have no impact on the treatment decision made by the physician.

8.5 Study size

The sample size calculation is based on the primary observational endpoint, which is the change from the baseline period (4-week baseline period) in the number of any hypoglycaemic episodes occurring during the 12-month observation period with Tresiba[®]. The change from baseline measure is operationalised as the mean of the per-patient paired differences in hypoglycaemic episodes/PYE.

For both T1DM and T2DM, the mean of paired differences is expected to be 1 episode/PYE with a standard deviation of 7 (a conservative estimate based on our understanding of possible variation in the measures). At $\alpha=0.05$ and 90% power, the number of patients who switch to Tresiba[®] and complete the 12-month observation period is $n_{T1DM}=n_{T2DM}= 517$. Assuming a 15% rate of withdrawal (loss of patient for any reason prior to completing 12-month observation period), 608 T1DM and 608 T2DM patients will need to be enrolled and complete the 4-week baseline period and switch to Tresiba[®] to achieve 517 T1DM and 517 T2DM patients completing the observation period.

The data from the participating countries will be pooled. Analysis on data from the patients in Germany up to the discontinuation date will be specified in the SAP.

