³ Patient diaries will include sections for recording information such as details of hypoglycaemia, insulin dosage, dose-time flexibility, and health economics resource use.

⁴ Each SADR will be spontaneously reported and recorded on a separate AE and safety information form according to existing reporting procedures. MESI includes medication errors.

⁵ Four weeks prospective hypoglycaemia assessment leading up to visits at Months 0, 3, 6, 9, and 12, in addition to a 6 month severe hypoglycaemia recall at visit 1.

⁶ Patients will be encouraged to fill the PRO questionnaires, preferably before any other study related procedures.

⁷ Status version of DSTQ at visits 1, 2, 3, 4, 5 and 6, change version of DSTQ at visit 6.

⁸ Preference of FlexTouch[®] over previous injection method.

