8.7.2.1 Analysis of primary endpoint

The primary observational endpoint is the change from the baseline period in the number of any hypoglycaemic episodes occurring during the 12-month observation period with Tresiba[®]. The count data will be converted to rates per PYE for analysis purposes.

For purposes of descriptive statistics, the endpoint will be calculated as the change in patient paired differences and will be summarised, by visit, as number of observations with available values, number of observations with missing values, mean (of paired differences), 95% CI of the mean, standard deviation, minimum, median, and maximum.

The primary endpoint will also be estimated as a baseline-adjusted change using an appropriate regression estimator (eg, negative binomial estimator) with additional covariates, along with the associated 95% CI and p-value. Additional covariates may be added to the model (e.g., clinical, country, etc.). The list of covariates to be included, along with the baseline endpoint value, will be specified in the SAP.

The baseline value for the primary endpoint is calculated from the entire 4-week baseline period.

Patients will be analysed separately based on being T1DM or T2DM patients who use insulin.

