8.7.2.2 Analysis of secondary endpoints

Analysis of secondary endpoints will be performed on the FAS. Secondary endpoints that are interval and ratio-level endpoints will be analysed in the same manner as the primary endpoint using an appropriate regression estimator.

The baseline value for number data is calculated in the same manner as for the primary endpoint. For all other endpoints the baseline is the value recorded at visit 2.

For the following categorical endpoints, data will be displayed in frequency tables as percentages with numerator counts, based upon the appropriate denominator:

- Any hypoglycaemia
- Responder for HbA1c:
 - HbA1c <7% at end of study
 - HbA1c <7.5% at end of study
 - HbA1c <7% at end of study without severe hypoglycaemic episodes during the last 12 weeks of treatment including only patients exposed for at least 12 weeks
 - HbA1c <7.5% at end of study without severe hypoglycaemic episodes during the last 12 weeks of treatment including only patients exposed for at least 12 weeks
 - HbA1c lowered according to national guidelines.

Additional exploratory hypothesis-generating analyses may also be performed as deemed relevant.

All statistical tests will be performed as two-sided tests with a significance level of 0.05.

Patients will be analysed separately based on being T1DM or T2DM patients who use insulin.

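### The planning SD of 7 episodes/PYE is not conservative: counting noise from 4-week diaries alone exceeds it once the mean rate passes about 3 episodes/PYE

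*Protocol*

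**What the plan says.** Section 8.5, repeated in the abstract at 3.8, sizes the study on a change "operationalised as the mean of the per-patient paired differences in hypoglycaemic episodes/PYE". For T1DM and T2DM alike, "the mean of paired differences is expected to be 1 episode/PYE with a standard deviation of 7 (a conservative estimate". The only support offered is the sponsor's own understanding of how much the measures might vary. "At $\alpha=0.05$ and 90% power", this gives 517 completers per diabetes type, raised to 608 for 15% withdrawal. Section 8.7.2.2 makes all tests two-sided at 0.05.

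The exposure behind each patient's rate is short. On baseline, section 8.7.2.1 says: "The baseline value for the primary endpoint is calculated from the entire 4-week baseline period". The footnote to Table 8–1 (section 8.2.6) gives the collection scheme: "Four weeks prospective hypoglycaemia assessment leading up to visits at Months 0, 3, 6, 9, and 12". Counts are then converted to rates per PYE.

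Sections 8.3.2.1 and 8.4.1 make the endpoint broad: symptomatic episodes with or without a glucose reading, plus asymptomatic readings at or below 3.9 mmol/L. No expected rate of such episodes is given for either diabetes type.

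**The concern.** Annualising a 4-week count multiplies it by 13, so a single baseline episode moves a patient's rate by nearly two of the assumed SDs. Whether an SD of 7 is achievable therefore depends on how often episodes occur, and the protocol does not say. A value called conservative should be safe over the plausible range of rates. This one leaves no margin unless episodes are very rare.

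The stated power rests on this SD, and so does the description of the study in section 8.1.2 as adequately powered. If the SD is too small, a reader of a null primary result may credit the study with a precision for a change of 1/PYE that it did not have.

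**Working it through.** **1. The protocol's own figure.** Inputs from section 8.5: difference 1, SD 7, two-sided alpha 0.05, power 90%.
- Normal approximation: n = (7 x (1.960 + 1.282) / 1)^2 = 514.9, so 515.
- Exact paired t: n = 517, with power 90.0% at 517.
- Withdrawal: 517 / 0.85 = 608.2, stated as 608.

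The calculation reproduces. What needs checking is the SD.

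**2. Poisson floor of the SD.** Exposure is 4/52 year at baseline (section 8.7.2.1) and at most four 4-week diaries, 16/52 year, after the switch (Table 8–1). For a Poisson count over time t, the annualised rate has variance (rate)/t. So

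Var(difference) = 13 x (baseline rate) + 3.25 x (on-treatment rate).

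With equal rates this is 16.25 x the mean rate (16.3 with 28/365.25 for four weeks). Setting it to 7^2 = 49 gives 49 / 16.25 = 3.02/PYE. With a drop of 1/PYE the limit on the baseline rate is (49 + 3.25) / 16.25 = 3.22/PYE.

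This is the average within-patient variance, so it depends only on the mean rate; many zero-count patients or a skewed distribution do not lower it. Over-dispersion within patients, and differences between patients in their true change, add to it.

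**3. What 3/PYE means.** The mean baseline diary holds 3/13 = 0.23 episodes, and exp(-0.23) = 79% of patients would record none if all shared that rate.

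**4. Other exposure readings (equal rates).**
- One on-treatment diary only: 49 / (13 + 13) = 1.9/PYE.
- A full year observed: 49 / (13 + 1) = 3.5.
- Baseline noise alone: 49 / 13 = 3.8.
- Baseline stretched to 6 weeks by the +14-day window (section 8.4.3), four on-treatment diaries: 49 / (8.67 + 3.25) = 4.1.

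Combining the 6-week baseline with a full observed year would give 49 / 9.67 = 5.1, but the diary schedule describes neither.

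**5. Power at the floor for a drop of 1/PYE.** SD = sqrt(13 x rate + 3.25 x (rate - 1)), noncentral t. The baseline rates are assumptions, because the protocol gives none.

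| Baseline rate/PYE | Floor SD | Power, n = 517 | Power, n = 608 | n for 90% |
|---|---|---|---|---|
| 2 | 5.4 | 99% | >99% | 308 |
| 3 | 6.75 | 92% | 95% | 479 |
| 4 | 7.9 | 82% | 88% | 649 |
| 5 | 8.8 | 73% | 80% | 820 |
| 10 | 12.6 | 44% | 50% | 1674 |
| 20 | 17.9 | 24% | 28% | 3381 |

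Simulation at n = 517 agrees: 94% at 3/PYE, 74% at 5, 43% at 10, 24% at 20. A gamma frailty common to both periods changes little.

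**6. Does a count model help?** Take a Poisson log rate ratio with SE = sqrt(1/(517 x rate x 4/52) + 1/(517 x (rate - 1) x 16/52)). Power is 97% at 3/PYE, 88% at 4, 78% at 5, 46% at 10 and 25% at 20. The gap narrows but remains.

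**The case against.** A reader might infer that the study simply fails to deliver 90% power. The protocol does not support that. It states no rate, and at a baseline of about 3.2/PYE or less the Poisson floor still allows 90%. Section 8.9 expects enrolment to lean towards patients with less hypoglycaemia, and section 8.3.2.6 limits glucose self-testing to site practice. Both could lower the recorded rate, though neither puts a number on it.

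The table also holds the drop at 1/PYE, which is only 10% at 10/PYE and 5% at 20. For a 20% fall, floor power with 517 patients is 95% at 10/PYE and above 99% at 20. For a 10% fall at 40/PYE it is 95%. Scaling does not rescue every case: it is 73% for a 20% fall at 5/PYE and 72% for a 10% fall at 20/PYE.

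The paired difference is the descriptive summary. On the inferential analysis, section 8.7.2.1 says "The primary endpoint will also be estimated as a baseline-adjusted change using an appropriate regression estimator (eg, negative binomial estimator" and so on. The full analysis set is everyone dosed, planned at 608 per type rather than 517. A 95% CI will be reported and will show the precision achieved, so a null result need not be misread.

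All of this stands, and it makes the loss of power conditional. None of it supports the word conservative, which claims safety across plausible rates when the SD is attainable only at low ones. The planned count model does not by itself remove the shortfall at higher rates.

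**Conclusion.** Wrong as written, in an input assumption. The sample-size arithmetic itself is correct. With the protocol's own diary lengths, an SD of 7 cannot be met once the mean rate exceeds about 3/PYE (about 1.9 to 4.1 across the single-change exposure readings). Even at 3/PYE it leaves no room for the over-dispersion that naming a negative binomial estimator anticipates. The same value is applied to T1DM and T2DM with no rate stated for either.

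How much power is lost depends on a rate the protocol does not give. For the protocol's own difference of 1/PYE it runs from no loss at 3/PYE or below to 44% power at 10/PYE and 24% at 20/PYE with 517 patients, in the best case. This assumes counts no less variable than Poisson, complete diaries and a paired-difference test. A general finding that the study is underpowered does not follow.

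**What to change.** Keep 608 switched patients per diabetes type. In sections 3.8 and 8.5:
- State the expected rate of any hypoglycaemic episode and its dispersion, separately for T1DM and T2DM.
- Replace the SD of 7 by a variance built from diary exposure: (baseline rate)/(4/52) + (on-treatment rate)/(16/52), plus over-dispersion and between-patient variation in change. Baseline diaries from one of the internal data cuts planned in sections 5 and 8.7.3 could supply the inputs.
- Restate the difference or rate ratio that 517 and 608 patients can detect at 90% power under the planned count regression.
- Delete the word conservative, and bring the power statements in sections 8.1.2 and 8.2 into line.

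The cost is a short recalculation and a wording change, with no extra patients or data. The downside is that the stated detectable effect may become less favourable.

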8.6 Data management

8.6.1 Data management

Data from individual patient's charts will be remotely collected through a password-protected web-based electronic data capture (EDC) system. The prescribing physician or an authorised and appropriately trained delegate will enter the data into the web-based eCRF based on the individual patient's charts. No source documents will be sent off-site. To protect privacy, data will be anonymised and processed in accordance with local regulations regarding privacy protection.

Data management is the responsibility of Data Management, Novo Nordisk Headquarters. Data management will be delegated under an agreement of transfer of responsibilities to [REDACTED]

Data must be loaded at least one time during the conduct of the trial and as well as after Database Lock into Novo Nordisk Clinical Data Management System (CDMS). Data must be in a loadable format for Oracle Clinical.

Appropriate measures such as encryption or deletion must be enforced to protect the identity of patients in all presentations and publications as required by local/regional/national requirements.

Appropriate measures such as encryption of data files must be used to ensure confidentiality of patient data when it is transmitted over open networks.

8.6.2 Case report forms and rules for completing

As used in this protocol, the term eCRF should be understood to refer to an electronic data record.

Novo Nordisk will provide a system for EDC. This system and support services for the system will be supplied by [REDACTED]. The activities of [REDACTED] will be under the direction and supervision of Novo Nordisk.

Pregnancy and MESI forms will be paper-based and will be supplied by Novo Nordisk.

An eCRF is required and should be completed for each included patient. The completed original eCRFs are the sole property of Novo Nordisk and should not be made available in any form to third parties except for authorised representatives of Novo Nordisk or appropriate regulatory authorities, without written permission from Novo Nordisk.

The treating physician has responsibility for the accuracy and authenticity of all clinical safety and laboratory data entered on the eCRFs. In most cases, the source documents are the physician's patient chart.

Ensure that all relevant questions are answered and that no empty data blocks exist.

If a test/assessment has not been done and will not be available, or if the question is irrelevant (eg, is not applicable) indicate this according to the instructions for completing eCRFs.

By signing the affirmation statement electronically, the physician confirms that the information is complete and correct.

Data will be anonymised and collected by physicians, or appropriately trained delegates, so no direct patient contact with Novo Nordisk or [REDACTED] staff is envisaged.

8.6.3 Corrections to case report forms (CRFs)

e CRF data can be corrected only by the physician or the physician's authorised staff. For PROs, the patient will be responsible for notifying the physician of any errors which can then be corrected in the eCRF by the physician or the physician's authorised staff. An audit trail will be maintained in the EDC application containing as a minimum: identification of the person entering the data, date and time of the entry and reason for the correction, the original entry and the corrected entry. If corrections are made by the physician's authorised staff after the date of the physician's signature on the affirmation statement, the statement must be signed again by the physician.

The following paragraphs apply to corrections to data on the paper-based MESI and pregnancy forms only.

Corrections to the data on the case report forms (CRFs) must only be made by drawing a straight line through the incorrect data and by writing the correct value next to data that has been crossed out. Each correction must contain initials, date and explanation (if necessary) by the physician or the physician's authorised staff. If corrections are made by the physician's authorised staff after the date of the physician's signature on the affirmation statement, the statement must be signed and dated again by the physician.

Corrections necessary after the CRFs have been removed from the physician's site must be documented on a Data Clarification Form (DCF). Such corrections must be approved by the physician or her/his authorised staff.

8.6.4 eCRF flow

The physician must ensure that data is recorded in the eCRFs as soon as possible after the visit (preferably within 5 days if source data is available otherwise in connection to the visit of obtaining data). When data is entered, it will be available to Novo Nordisk for data verification activities.

When the final non-interventional study report is available, the data will be archived by Novo Nordisk.

8.7 Data analysis

8.7.1 Evaluability of patients for analysis

All observational endpoints will be analysed on the FAS. The FAS includes all patients who received at least 1 dose of Tresiba[®] at visit 2. Patients who complete visit 1 but do not initiate Tresiba[®] at visit 2 will be excluded from the analyses.

The safety population will consist of all patients who received at least 1 dose of Tresiba[®] (FAS).

Patients will be analysed separately based on being T1DM or T2DM patients who use insulin.

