3.4 Study design

This is a 12-month, multi-centre, prospective, non-interventional study assessing the safety and effectiveness of Tresiba[®] 100 units/mL or Tresiba[®] 200 units/mL OD, used with any other anti-diabetic treatment according to local label, in patients with T1DM or T2DM where the physician has decided to start the patient on Tresiba[®] treatment. This is under the category of post-authorisation safety study (PASS).

The study is expected to be conducted within the following countries: Denmark, Germany, The Netherlands, Spain, Sweden, Switzerland, Italy, and the United Kingdom (UK).

Novo Nordisk ceased the distribution of Tresiba[®] in Germany at the end of September 2015. Germany will be removed from this study, thus patients enrolled in Germany based on the protocol version 2.0 will be discontinued. Data obtainable up to the discontinuation date will be included in the analyses, as appropriate and specified in the Statistical Analysis Plan (SAP).

Patients with T1DM and T2DM who are treated with insulin will be followed for a minimum of 4 weeks before (baseline period), and a maximum of 12 months after switching to Tresiba[®] (observation period).

As indicated in the Summary of Product Characteristics (SmPC), close glucose monitoring is recommended during the transfer from other insulin medicinal products and in the following weeks (2). Using patient diaries, prospective clinical assessments for hypoglycaemia will occur leading up to Months 0, 3, 6, 9, and 12. Visit 1 (-4 weeks) initiates the baseline period; physicians who plan to

start Tresiba[®] treatment, as part of standard clinical practice, begin evaluating the patients treatment needs based on reviewing diaries on hypoglycaemia and glycaemic control, in order to confirm their treatment decision to switch to Tresiba[®]. At visit 2 (0 months) only those patients who are switched to Tresiba[®] treatment are entered into the observation period. In clinical practice, some patients will switch insulin treatment immediately because they require instant changes to their treatment for safety or for effectiveness reasons. Other patients will after evaluation not change treatment at all. And again, other patients will be evaluated, and this will then reveal that their situation may actually be improved by changing treatment regimen. This baseline period will provide a portrait of the patient's risk of developing hypoglycaemia.

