8.2.1 Number of patients to be studied

Patients with T1DM or T2DM, eligible for this study will be included. All data collected will be included in the analysis.

Planned number of patients to be included: 1216 patients are expected to switch treatment to Tresiba[®] following the 4-week baseline period, including the patients from sites in Germany, according to the SAP.

Planned number of patients to complete the study in the participating countries: in total, 1034 are planned to complete the study (based on a withdrawal rate of 15%).

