8.7.2.3 Additional analyses

It is possible that if a patient experiences a severe episode of hypoglycaemia during the 4-week baseline period, the treating physician may elect to switch them immediately to Tresiba[®] (or another product), making that patient ineligible to continue in this study. This could affect estimation of the change from baseline in hypoglycaemic episode rate as the baseline measure could be underestimated, thus making it harder, *ceteris paribus*, to get a large effect from Tresiba[®] during the observation period (ie, large change from baseline, because the baseline rate was lower than it should have been). Consequently, the baseline rates of patients who are switched early to Tresiba[®] will be examined. If there is sufficient evidence that the omission of these patients biases baseline rates, appropriate methods may be employed (eg, weighting data for patients included in the study)

to adjust data of the patients enrolled in the study. Details for these analyses will be provided in the SAP.

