8.9 Limitations of the research methods

The enrolled patients in the current non-interventional study are acting as their own control. Thus, the baseline period of 4 weeks prior to planned initiation of Tresiba[®] is crucial in order to obtain reference data for the enrolled patients. The baseline period also constitutes an evaluation period for the physician, in order to aid in the final decision whether to initiate Tresiba[®]. While no causal

relationships can be concluded based on a non-interventional study design, the aim is to explore the associations between Tresiba[®] and other anti-diabetic treatment regimens with regard to any hypoglycaemic episodes.

The absence of a comparator group results in a number of threats to internal validity of the study design, the most critical of which is that the design will not provide the ability to rule out many alternative explanations for changes from baseline.

Whilst this is a study of real world clinical practice, enhanced glucose monitoring during the 4-week baseline period may potentially bias the physician's decision to commence Tresiba[®] treatment. More frequent blood glucose monitoring and maintaining a diary is an important factor in improved blood glucose control. Based on the enhanced monitoring and hypoglycaemic episode data collected during the 4-week baseline period, patients who the physician considered candidates for a treatment switch to Tresiba[®] at visit 1, may have improved blood glucose control and, at visit 2, may no longer be considered candidates for switching treatment.

Furthermore, due to data collection procedures conducted at visit 1 (see [Table 8-1](#)), it is possible that treating physicians may selectively enrol only those patients deemed, by past medical history, to be less likely to experience a hypoglycaemic episode during the 4-week baseline period before switching to Tresiba[®]. This differential selection of patients introduces a form of systematic selection bias that will result in an underestimation of the true rate of hypoglycaemia among all T1DM and T2DM patients switched to Tresiba[®]. The impact of this type of selection bias is that rates obtained from this study population will represent only those patients with an a priori lower rate of hypoglycaemia.

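### Non-switching after a quiet baseline diary can produce a false fall in hypoglycaemia; the protocol gives, and remedies, only the opposite direction of selection bias

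*Protocol*

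**What the plan says.** - **Use of the diary.** Section 3.4 says that physicians "begin evaluating the patients treatment needs based on reviewing diaries on hypoglycaemia and glycaemic control, in order to confirm their treatment decision to switch". Section 8.7.2.1 takes the baseline value of the primary endpoint from the same full 4-week period. Section 8.9 confirms that each patient is their own control and that there is no comparator group.
- **Exclusion.** Section 8.7.1: "Patients who complete visit 1 but do not initiate Tresiba[®] at visit 2 will be excluded from the analyses".
- **Non-switchers.** Section 8.9 notes that patients whose control improves under closer monitoring, "at visit 2, may no longer be considered candidates for switching treatment". It presents this as an influence on the physician's decision and does not say what it does to the change from baseline.
- **Early switchers.** Sections 8.7.2.3 and 8.9 say that patients switched at once after a severe episode leave the study, that baseline may then be underestimated, and that a large effect becomes harder to show. Section 8.7.2.3 plans to examine early switchers' baseline rates. If there is enough evidence of bias, "appropriate methods may be employed (eg, weighting data for patients included in the study" and similar, with details left to the SAP.
- **Planned effect.** Section 8.5: "the mean of paired differences is expected to be 1 episode/PYE with a standard deviation of 7".

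**The concern.** Inclusion in the analysis depends partly on a short, noisy count, and the later rate is then compared with that same count. Dropping patients because the count was low leaves a group whose counts were, on average, high by chance. Regression to the mean then looks like benefit. With a single arm, no control group shows the same drift, and using baseline as a covariate in the regression does not remove it from a before-after comparison.

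The protocol attaches a direction only to the opposite mechanism. A reader of 8.7.2.3 and 8.9 would conclude that selection at the switch makes an observed reduction conservative. That conclusion is not secured.

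**Working it through.** **1. The plan's own figure.** Inputs from 8.5 and 8.7.2.2: difference 1, SD 7, two-sided 0.05, power 90%, withdrawal 15%. The normal formula gives ((1.960 + 1.2816) × 7/1)² = 514.9. The noncentral t gives n = 517 with power 0.9001. Then 517/0.85 = 608.2. Both 517 and 608 reproduce.

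**2. Noise in the baseline.** One episode in 28 days is 365.25/28 = 13.0/PYE. One episode over four 4-week follow-up diaries (112 days) is 3.26/PYE. With Poisson noise alone, the variance of the paired difference is m × (13.04 + 3.26) = 16.3m. An SD of 7 therefore allows a mean rate m of at most 49/16.3 = 3.0/PYE. Higher rates below show the range.

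**3. False change from non-switching, no drug effect.** Assumptions not in the protocol: patient rates are gamma with mean m and shape k; a fraction a of empty-diary patients and b of the others switch. With T = 28/365.25 = 0.0767:

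- share with an empty diary: p0 = (k/(k + mT))^k
- their mean true rate: r0 = k/(k/m + T)
- share switched: D = b − (b − a)p0
- switchers' observed baseline: bm/D
- switchers' follow-up rate: (bm − (b − a)p0·r0)/D
- false change: −(b − a)p0·r0/D

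Example: m = 3, k = 1, a = 0.90, b = 1 gives p0 = 0.813, r0 = 2.44, D = 0.919. Baseline is 3.27, follow-up 3.05, change -0.22.

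| Mean rate/PYE | 90% vs 100% switch (k = 0.5; 1) | 70% vs 95% switch (k = 0.5; 1) |
|---|---|---|
| 3 | -0.19; -0.22 | -0.57; -0.66 |
| 5 | -0.23; -0.28 | -0.70; -0.85 |
| 10 | -0.26; -0.34 | -0.78; -0.99 |
| 20 | -0.26; -0.32 | -0.74; -0.92 |
| 40 | -0.22; -0.25 | -0.61; -0.68 |

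**4. Effect on the test.** At 3/PYE, if 25% of empty-diary patients are not switched (20–21% of all patients), the false change is -0.45 to -0.75, for shape 0.3 up to no heterogeneity. The chance of p < 0.05 at n = 517 is then about 28–62% instead of 5%. A false change equal to the whole planned effect needs about 25–37% of all patients not to be switched.

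**5. The opposite mechanism.** Patients with a severe baseline episode are removed; the severe shares are assumed. At 3/PYE with 2% of episodes severe, this alone gives +0.06, and combined with step 4 the change is -0.38 to -0.67. At 40/PYE (k = 1, non-switching among patients with 0–1 episodes) the net can reverse:

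| Not switched among quiet diaries | Episodes severe | Net change | After weighting for early switchers |
|---|---|---|---|
| 10% | 2% | +0.39 | -0.38 |
| 25% | 2% | -0.24 | -1.03 |
| 25% | 5% | +0.79 | -1.04 |

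Weighting here restores the removed early switchers on the observed baseline count. With early switching alone it brought the bias to about zero. With both mechanisms it returned the estimate to the value for non-switching alone.

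**6. The weighting target.** An early switcher's baseline ends at the triggering episode. In simulation at a true mean of 10/PYE, early switchers had true rates of 20–30/PYE but observed rates of 77–85 averaged per patient (46–55 pooled). Weighting to the per-patient target put the cohort baseline at 10.6–10.7 instead of 10.

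**7. What selection acts on.** These are simulated rate ratios at shape 0.7; the truth is 1.

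| Selection depends on | Switchers only | Joint model with all baseline diaries |
|---|---|---|
| Diary count (70% vs 95%) | 0.88 at 5/PYE, 0.93 at 10, 0.99 at 40 | 1.00–1.01 |
| Stable underlying rate | 0.99–1.00 | 1.09 at 3 and 5/PYE, 1.06 at 10 |

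**The case against.** The case on the other side is substantial, and several stronger readings fall to it.

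- **That the protocol overlooks non-switching.** It does not. Section 8.9 describes it, warns in general terms that alternative explanations cannot be ruled out, and disclaims causal conclusions. What is missing is the direction of this bias.
- **That the net bias favours Tresiba, at the size of the planned effect.** The document gives no switch shares. Early switching offsets the bias and can reverse it at high rates. Rates well above 3/PYE also do not fit the planned SD of 7, so setting those biases against the planned 1/PYE mixes settings.
- **That weighting adds bias and should be deleted.** It is conditional, offered as an example, and deferred to the SAP. For the problem it addresses, it works. The remaining worries are narrower: it removes an offset while leaving non-switching uncorrected, and nothing yet guards against a target taken from shortened baselines.
- **That including all diaries makes selection ignorable.** This holds only if selection depends on the observed diary. Physicians also see glycaemic control and history. If they act on the patient's stable rate, the switcher-only analysis is unbiased and the joint model is biased against Tresiba.
- **That 8.2.1 contradicts 8.7.1.** "All data collected will be included in the analysis" is a general sentence governed by the specific rule in 8.7.1. It deserves rewording and no more.

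Sensitivity analyses usually belong in the SAP. The exclusion rule and the one-sided statement of direction, however, are fixed in this protocol.

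**Conclusion.** The point holds in a limited form. Every link needed for regression to the mean is in the protocol: the diary informs the switch, non-switchers are excluded, the diary is the comparator, and there is no control group. The only direction given for bias in the change from baseline is the conservative one.

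Under no drug effect, the non-switching component is about -0.2 to -0.35 episodes/PYE with mild selection and -0.6 to -1.0 with stronger selection, against a planned 1. These figures rest on assumed rates, gamma heterogeneity and switch shares, and on selection through the diary count. The bias disappears if selection follows the stable underlying rate. The net direction after early switching cannot be determined from the document. The supportable conclusion is therefore that a reduction may not be described as conservative with respect to selection, and that the data needed to judge it should be secured.

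**What to change.** 1. In 8.7.2.3 and 8.9, state that selection at visit 2 can bias the change from baseline in either direction, and stop describing it as only conservative.
2. Extend the planned check of early switchers in 8.7.2.3: tabulate baseline rates, with actual diary exposure, for switchers, non-switchers and early switchers, beside the reasons for switching or not that 8.3.3.2 already records.
3. Add a sensitivity analysis: a count model with a patient random effect that includes every available baseline diary. Non-switchers contribute baseline only; early switchers contribute their shortened baseline with its true exposure. Report it next to the switcher-only result, and say that it is valid only if selection depends on the observed diary.
4. Keep weighting as an option, but require that it address both exclusions and that its target not be the early switchers' rate over a baseline ending at the triggering episode.
5. Reword the sentence in 8.2.1 so that it defers to 8.7.1.

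The cost is some wording and one extra model. Section 8.4.4 already has diaries collected at visit 2. The practical burden is making sure that sites enter non-switchers' baseline diaries in the eCRF, because these may be hard to recover later.
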